4.1.5. Randomization Procedures (~1 week)

Once a participant meets all eligibility criteria they will be randomized, and the device shipment will occur thereafter. Participants will need to watch a video on how to set-up and use the Mi-Helper device. Once the training is completed, the participant will be able to review the study training video at any time within the Study App.

A total of 156 participants will be randomized equally to one of two groups:

- Group I (active treatment): 10 LPM, dehumidified air, 15 minutes total
- Group II (sham [control] treatment): 2 LPM, ambient air administered intermittently via Mi-Helper, 15 minutes total

Upon receipt of the Mi-Helper device, the participant will be instructed to store the shipment at room temperature and to not open the desiccant cartridge and tube set prior to use. The training will also instruct the participants that the device may only be used 'once', during a qualifying migraine attack. A

qualifying migraine attack must meet the following criteria based on responses to the Baseline Questionnaire:

- Migraine head pain is at least mild intensity (score of 1=mild, 2=moderate, or 3=severe on the 4-point VRS).
- Onset of migraine head pain was no more than one hour prior to treatment.
- Participant did not wake up with the migraine attack.
- Participant is not experiencing severe sinus congestion.
- Participant did not have migraine related pain in the 48 hours prior to the migraine attack.
- Participant did not take any migraine rescue medications in the 48 hours prior to the migraine attack, such as triptans, NSAIDs, or gepants used for acute treatment.

The participant may reach out to the study team via the Study App, email, or phone to address any questions they have about any study-related procedures.

Participants will have up to 35 days to complete the treatment session after receiving the device.

4.1.6. Baseline Procedures (pre-treatment)

Baseline assessments will be initiated at the onset of a migraine attack. Baseline assessments will include questions about the participant's head pain, nausea, photosensitivity, phonosensitivity, and the most bothersome symptoms (MBS) which will be recorded within the Study App prior to treatment initiation.

4.1.7. Treatment Procedures (48 hours)

Participants will be instructed to use the Mi-Helper device once their migraine head pain has reached at least mild intensity. This will be determined by their response to the question about their head pain within the Study App. Participants will be instructed to use the Mi-Helper within 1 hour from the time of migraine head pain onset.

Once the migraine headache score is recorded as being mild to severe (score of 1 to 3 recorded on the 4-point VRS scale) and the participant has confirmed that they have not used any acute migraine medications in the last 48 hours, the Study App will instruct the participant to initiate treatment with the Mi-Helper device and dose treatment (active or sham) for a total of 15 minutes based on their group allocation. Participants will be advised against using any rescue medication until collection of the Migraine Symptom Questionnaire at 2 hours post-treatment with the Mi-Helper device. However, if participants do need to administer rescue treatment after administering treatment with Mi-Helper, they will need to report this using the 'Rescue Medication Form' within the Study App. Use of rescue medication within 2 hours of treatment will be considered a treatment failure. In the instance that abortive treatments have been used 48-hours prior to the start of treatment or the time of onset of migraine head pain exceeds 1 hour, the participant will need to wait until their next migraine episode of at least mild intensity, to use the device.

Participants will be instructed that they may stop treatment if they are unable to tolerate it by moving the nebulizer away from their nose, and report this within the Study App.

Participants will be required to respond to questions about their head pain, nausea, photosensitivity, phonosensitivity, and the most bothersome symptom (MBS) within the Study App immediately post-treatment and then at 2 hours, 24 hours and 48 hours post-treatment.

At 2 hours post-treatment, participants will also be required to respond to questions about the device tolerability and user experience questionnaire. Select user experience questions will be repeated in the 24-hour assessment.

Participants can report any changes in their health through the Study App while participating in this study.

If migraine symptoms have not resolved, participants will be able to use rescue medication between the 2-to-48-hour period after using the device. Participants will be instructed to report rescue medication use in the 'Rescue Medication Form' within the Study App. This form will be available for participant use during the entire post-treatment period through the Study App and will not be timepoint bound.

4.1.8. End of Study Procedures

All participants will receive a single treatment with the Mi-Helper device. After completing the 24-hour assessment, they will be prompted to return the device body utilizing the packaging and prepaid shipping labels provided within the original device shipment.

Participation in the study will be complete once the participant completes the 48-hour questionnaire and returns their device.

4.2. General Study Population

Participants need to meet the following eligibility criteria to be considered for enrollment in this study.

4.2.1. Inclusion Criteria

To be eligible for participation in this study, a participant must meet all the following criteria:

1. Age of 18 to 70 years, inclusive, of either sex at birth.
2. Lives in the contiguous United States.
3. Self-reported to be able to read and understand English sufficiently to provide informed consent.
4. Individual has had a diagnosis of migraine with or without aura for at least 1 year.
5. Experiences 2 to 8 migraine attacks per month documented via migraine eDiary during screening.
6. Migraine onset before 50 years of age, self-reported during screening.
7. Migraine preventive medication unchanged for 4 weeks prior to study enrollment.
8. Stated willingness to comply with all study procedures and availability for the duration of the study.
9. Individual owns a functioning smartphone device, internet connection (Wi-Fi or data plan) and are willing to download the Study App

4.2.2. Exclusion Criteria

A participant who meets any of the following criteria will be excluded from participation in the study:

1. Participant has difficulty distinguishing his or her migraine attacks from other types of headaches such as tension, exertion, cluster, hormonal or sinus headaches.
2. Participant has 15 or more headache days per month reported via migraine eDiary and during screening.
3. Participant using any opioid medication at the time of screening.

4. Participant has received Botox treatment, barbiturates, SPG block, nerve blocks or trigger point injections in the head or neck within the last 4 weeks of screening.
5. Participant lives at an altitude of 2000 meters or more above sea level.
6. Self-reported intolerance to intranasal therapy.
7. Self-reported recurrent epistaxis or chronic rhinosinusitis.
8. Self-reported sinus or intranasal surgery within the last 4 months of screening.
9. Self-reported history of 'complicated migraine or headaches' (i.e., hemiplegic migraine, ophthalmoplegic migraine, migrainous infarction, basilar migraine, post-traumatic headaches, post-concussion syndrome).
10. Known or suspected pregnancy as self-reported by the prospective participant at the time of screening.
11. Prospective participant is unable to fully understand the consent process and provide informed consent due to either language barriers or mental capacity.
12. Self-reported diagnosis of alcohol or substance abuse disorder at the time of screening.
13. Participant with active chronic pain syndromes, such as fibromyalgia, chronic pelvic pain, or complex regional pain syndrome (CRPS); or other pain syndrome like trigeminal neuralgia.
14. Participant with severe psychiatric conditions (such as major depressive episode, bipolar disorder, major depressive disorder, schizophrenia), dementia, or significant neurological disorders (other than migraine) that, in the Investigator's opinion, might interfere with study assessments.
15. Failure to adhere to or inability to complete Study App inputs and onboarding activities during the screening period. Participants who are not adherent during the screening period are not eligible for study entry.
16. Participation in a previous clinical study with the Mi-Helper device.
17. Participated in a migraine study or any interventional clinical study within the 3 months prior to screening.
18. Participant has an uncontrolled medical issue at the time of screening.
19. Any condition for which transnasal air flow would be contraindicated, as determined by the PI.

4.3. Randomization and Blinding

For this study, a total of 156 participants will be randomized equally into two groups. 1:1 randomization will be performed with a block size of 6, and stratified by gender to ensure balance with regards to gender.

- Group I (active treatment): 10 LPM, dehumidified air, 15 minutes
- Group II (sham [control] treatment): 2 LPM, ambient air administered intermittently via Mi-Helper, 15 minutes total

Balance between the two arms will be evaluated and confirmed using standardized mean differences (SMD), where absolute SMD values less than 0.2 will be considered as indicating good balance on a given variable or confounder. For variables that have an absolute SMD larger than 0.2, adjustments may be made to minimize any possible imbalance on those variables using multivariable analysis.

Participants will be randomized in a 1:1 fashion, with stratification for gender. The randomization schema for this study will be implemented within the ObvioGo platform.

5. SAMPLE SIZE CALCULATION

The sample size for this study was calculated to test the null hypothesis with a two-tailed Fisher's exact test.

The sample size is calculated to test the null hypothesis with 80% power at a 5% level of significance using PASS 2024 software, version 24.0.2.

If we assume that 41% of the participants in the active treatment arm will have pain freedom at 2 hours post treatment versus 16% in the sham arm, then 116 evaluable participants are required (58 per group). Allowing for a 25% dropout rate, a total of 156 (78 active versus 78 sham) participants should be enrolled in the study.

6. GENERAL ANALYSIS CONSIDERATIONS

6.1. Analysis Populations

For the purposes of analysis, the following analysis sets are defined:

6.1.1. *Intent-to-Treat (ITT) Population*

- All participants who were randomly assigned to a treatment.

6.1.2. *Modified Intention to Treat (mITT) Population*

- All participants who used the study intervention and completed a baseline and 2-hour post-dose pain assessment.

6.1.3. *Per Protocol (PP) Population*

- All participants in the mITT population that do not have a major protocol deviation related to primary endpoint(s), and completed the primary endpoint(s) and completed the treatment in compliance with the protocol, with group assignment as treated.

The ITT analysis set will serve as the main analysis set for all safety evaluations.

The mITT analysis set will be the primary population used for efficacy analyses in this study.

The primary and secondary efficacy assessments will also be performed on the PP and the ITT analysis sets as a sensitivity analysis.

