## 7.4 Concomitant Diets, Treatments, and Medications

Participants are prohibited from using their acute migraine medications within 48 hours prior to using the Mi-Helper device. Acute medication may include over-the-counter medications like non-steroidal anti-inflammatory drugs (i.e., aspirin or ibuprofen) and acetaminophen; prescription medications like triptans (i.e., sumatriptan, zolmitriptan, etc.), gepants

(ubrogepant, Rimegepant,etc.), antiemetics (metoclopramide, prochlorperazine, or promethazine); or another medical neuromodulation device like Cefaly®.

Participants should continue to take any prescribed migraine preventive medications as instructed by their physician.

Participants may use rescue medication(s) after administering treatment with Mi-Helper, however, rescue medication used within 2 hours of treatment will be considered a treatment failure. Participants will be advised against using their rescue medication until collection of the Migraine Symptom Questionnaire at 2 hours post-treatment. An ad hoc rescue medication form will be available on the Study App's dashboard after administration of study treatment (control or active) for participants to fill out if they decide to use rescue medication(s) prior to collection of the Migraine Symptom Questionnaire at 2-hours post-treatment. They will be asked about their migraine symptoms when they fill out the ad hoc rescue medication form.

No dietary restrictions are required for this protocol.

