## 11.3 Populations for Analyses

- **Intent-to-Treat (ITT) Population** – all participants who were randomly assigned to a treatment.
- **Modified Intention to Treat (mITT) Population** – all participants who used the study intervention and completed a baseline and 2-hour post-dose pain assessment.
- **Per Protocol (PP) Population** – all participants in the mITT population who do not have a major protocol deviation related to primary endpoint and complete the treatment in compliance with the protocol, with group assignment as treated, and have no use of rescue medication within 2 hours post treatment.

The ITT analysis set will serve as the main analysis set for all safety evaluations.

The mITT analysis set will be the primary population used for efficacy analyses in this study.

The primary and secondary efficacy assessments will also be performed on the PP and the ITT analysis sets as a sensitivity analysis.

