3.1.2. Secondary Objectives

- To determine the effect of Mi-Helper therapy on the most bothersome symptom (MBS) other than headache post treatment completion.
- To assess sustained pain freedom from 2 to 24 hours post treatment completion without the use of rescue medication
- To determine the proportion of participants reporting pain relief after Mi-Helper therapy without the use of rescue medication.

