3.2. Endpoints

3.2.1. Primary Efficacy Endpoint

- Pain freedom (PF) at 2 hours post-treatment completion (defined as reduction in headache severity from mild/moderate/severe pain at baseline to no pain at 2 hours after treatment completion). Use of rescue medication prior to 2 hours post treatment completion will be considered a failure for this endpoint (i.e. patient will be assigned the status of no reduction).

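### mITT drops a treated participant with recorded rescue before 2 hours and no 2-hour score, although the plan already defines that participant as a primary-endpoint failure; the two PP definitions also differ on rescue

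*SAP*

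**What the plan says.** **Endpoint.** SAP 3.2.1 states: "Use of rescue medication prior to 2 hours post treatment completion will be considered a failure for this endpoint". SAP 8.1 and protocol 11.6.1 repeat the rule.

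**Primary efficacy set.** SAP 6.1.2 defines mITT as "All participants who used the study intervention and completed a baseline and 2-hour post-dose pain assessment". Protocol 11.3 has the same condition: "all participants who used the study intervention and completed a baseline and 2-hour post-dose pain assessment". Neither makes an exception for rescue. Both documents name mITT as the primary population for efficacy.

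**How rescue is recorded.** SAP 4.1.7 describes a rescue form "available for participant use during the entire post-treatment period through the Study App and will not be timepoint bound". Protocol 7.4 offers an ad hoc form before the 2-hour questionnaire and adds: "They will be asked about their migraine symptoms when they fill out the ad hoc rescue medication form". Nothing says that these answers replace the 2-hour assessment. In SAP Table 1 the 2-hour pain freedom row lists only the baseline and 2-hour questionnaires as sources.

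**Who should answer at 2 hours.** Everyone: "Participants will be required to respond to questions about their head pain, nausea, photosensitivity, phonosensitivity" (SAP 4.1.7), with 2 hours among the required times.

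**PP.** Protocol 11.3 requires no rescue within 2 hours after treatment. SAP 6.1.3 has no rescue clause.

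**Missing data.** SAP 6.2 rules out imputation in one general sentence. SAP 8.1 counts a missing 2-hour score in the ITT sensitivity analysis as not pain free, for the primary endpoint only.

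**Secondary endpoints.** SAP 6.1 also runs these on ITT and PP. SAP 4.1.7 says generally that "Use of rescue medication within 2 hours of treatment will be considered a treatment failure", and one objective in SAP 3.1.2 is "To determine the proportion of participants reporting pain relief after Mi-Helper therapy without the use of rescue medication". The definitions of 2-hour MBS freedom and 2-hour pain relief (SAP 3.2.2 and Table 1) do not mention rescue.

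**The concern.** Membership of mITT depends on a post-randomisation event that can occur after the primary outcome has already been decided. Someone who rescues at one hour, completes the rescue form and ignores the later questionnaire is a known failure, but the set definition treats that person as having no outcome. Removing known failures raises the observed rate in whichever arm loses them. If the arms lose different numbers, the comparison that opens the whole hierarchy is biased, and the direction cannot be known in advance.

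The PP set has a related problem. Under the protocol wording it removes people for a reason that is itself a primary-endpoint failure, so PP pain freedom is conditioned on outcome. Under the SAP wording it does not. Two programmers working from the two documents would build different sets.

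**Working it through.** **1. The plan's own figure.** Inputs (protocol 11.1, SAP 5): 41% v 16%, two-sided Fisher's exact test, 5% level, 80% power. Exact enumeration gives power 0.8075 with 57 per arm and 0.817 with 58. The continuity-corrected formula gives 58 per arm. Dropout: 58/0.75 = 77.3, so 78 per arm and 156 in all. The stated 116 and 156 reproduce, so sample size is not at issue.

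**2. Test.** Pearson chi-squared without continuity correction, 1 df: X² = (a/n₁ − b/n₂)² / [p̄(1 − p̄)(1/n₁ + 1/n₂)], with p̄ = (a + b)/(n₁ + n₂). The whole-number counts nearest the planned rates are 24/58 and 9/58. Then p̄ = 33/116 = 0.2845, the difference is 15/58 = 0.2586, and X² = 0.06688/0.00702 = 9.53, p = 0.0020.

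**3. Restoring omitted failures.** If k treated rescue failures were left out of an arm, the numerator stays and the denominator grows by k. The documents give no k. Totals of 2, 4, 8 and 15 are assumed for illustration and are not bounds. Each range runs from all k in sham to all k in active.

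| k | mITT shows 24/58 v 9/58 (p=0.0020) | mITT shows 19/58 v 9/58 (p=0.030) |
|---|---|---|
| 2 | 0.0014 to 0.0031 | 0.023 to 0.039 |
| 4 | 0.0010 to 0.0045 | 0.018 to 0.0502 |
| 8 | 0.0005 to 0.0088 | 0.011 to 0.078 |
| 15 | 0.0001 to 0.023 | 0.0046 to 0.145 |

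An even split of 8 in the right-hand column (19/62 v 9/62) gives p = 0.032.

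**4. Tipping points against sham 9/58.** Smallest number of active-only failures that brings p to 0.05 or above:

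- 18/58 (p=0.048): 1, since 18/59 v 9/58 gives p = 0.054
- 19/58: 4 (p = 0.0502)
- 20/58 (p=0.018): 8 (p = 0.052)
- 22/58 (p=0.0064): 15 (p = 0.0505)
- 24/58: 23, since 24/81 v 9/58 gives p = 0.054

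The last exceeds the 78 − 58 = 20 per arm that the plan's dropout allowance leaves without an outcome. In the other direction, 17/58 v 9/58 has p = 0.075, and four restored sham failures (17/58 v 9/62) give p = 0.049.

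**5. Planned ITT sensitivity analysis.** With all 20 per arm counted as failures, 24/78 v 9/78 gives p = 0.0033 and 19/78 v 9/78 gives p = 0.037.

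**6. Protocol PP.** Those removed are all failures, so an arm's rate becomes p/(1 − r), where r is its early-rescue share (assumed; not in the documents). The starting odds ratio is (0.41/0.59)/(0.16/0.84) = 3.65.

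| r active / sham | PP rates | OR |
|---|---|---|
| 5% / 15% | 43.2% / 18.8% | 3.27 |
| 20% / 20% | 51.2% / 20.0% | 4.21 |
| 10% / 30% | 45.6% / 22.9% | 2.82 |

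Equal rescue shares still move the odds ratio, because the set is selected on outcome.

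**7. Secondary endpoints in ITT.** With no failure rule, a participant without a 2-hour questionnaire contributes nothing to 2-hour MBS freedom or pain relief. If 116 of 156 answer, the other 40 drop out and the analysis rests on essentially the mITT participants.

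**The case against.** The affected group is narrow: device used, rescue before 2 hours, rescue recorded elsewhere, and a required 2-hour questionnaire not given. It may be empty. The ITT sensitivity analysis already scores this person as a failure, and at the planned effect it agrees with mITT. Reversals need both a near-border table and a lopsided split. All of this stands, and it limits the weight of the point. It does not justify a primary set that omits settled outcomes. Nor does ITT isolate them, because it counts everyone without a 2-hour score as a failure, whatever the reason, and it does not open the fixed sequence.

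Three stronger readings are tempting and are not supported:

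- *A reader might infer that mITT drops all early rescue users.* It does not. Those who also give a 2-hour score stay in as failures.
- *A reader might infer that SAP 6.2 and 8.1 contradict each other.* They are better read as a general rule and a specific, named exception. What remains is the absence of any failure rule for the secondary endpoints in ITT, which affects sensitivity analyses only.
- *A reader might take the loss from 137 to 128 between the safety and mITT sets of the earlier four-arm study (protocol 3.2) as the size of this group.* The reasons for that loss are not given, so it cannot be used that way.

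**Conclusion.** The gap in mITT is certain on the current text of both documents; its effect is unknown. It touches the primary test only if someone has recorded early rescue and no 2-hour score. At the planned effect the conclusion is safe. Near the 5% border, one to four cases lying in one arm can change it, in either direction. These figures rest on assumed counts and on 58 per arm in mITT. The documents do not support a claim that the bias favours the device, or that the result would be reversed.

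The PP mismatch is also certain. It concerns a sensitivity analysis, and its size depends on rescue rates that the documents do not give. The point should be fixed before unblinding, so that nobody has to decide afterwards who counts.

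**What to change.** Before unblinding:

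- **mITT (protocol 11.3, SAP 6.1.2).** Define it as randomised participants who used the device, gave a baseline pain score, and have either a 2-hour pain score or rescue use recorded before 2 hours after the end of treatment. Score the latter as not pain free on the primary endpoint. Add the rescue questionnaire to the sources for 2-hour pain freedom in SAP Table 1.
- **PP.** Use one definition in both documents, preferably without the early-rescue exclusion. If the exclusion is kept, do not present PP pain freedom as a robustness check.
- **Missing data.** Make SAP 6.2 subject to 6.1.2 and 8.1. In the ITT sensitivity analysis, count missing binary secondary endpoints as not achieved.
- **Rescue in the 2-hour secondary endpoints.** State one rule for MBS freedom and for pain relief that applies to every mITT member, with or without a 2-hour score. Which rule is a choice of estimand for the sponsor.

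Cost: the protocol change is an amendment and needs IRB approval unless it qualifies as administrative (protocol 12.2), plus SAP edits. No new data or participants are needed, because rescue use is already collected. Observed response rates may be slightly lower. If nobody falls in the affected group, the primary result does not change.
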